4.0 Objectives of the Clinical Investigation

4.1 Objective

The objective of the study is to evaluate the safety and effectiveness of the Zenith Low Profile AAA Endovascular Graft used in conjunction with the Zenith

Spiral-Z AAA Iliac Leg Graft. The safety endpoint will be freedom from MAEs at 30 days and the effectiveness endpoint will be device success at 12 months.

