4.2 Claims and Intended Performance that are to be Verified

The following data points will be evaluated to verify device performance:

- Device success (including technical success)
- Procedural times
- Access method (percutaneous, cutdown, or conduit usage) employed during the procedure
- Clinical utility measures
- Morbidity, including Major Adverse Events (MAEs) as well as events distal to the graft limb (e.g., arterial thrombosis)
- Reinterventions-
- Endoleak, change in aneurysm size, migration, device patency, device integrity

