8.0 Design of the Clinical Investigation

8.1 Type of Investigation

The current investigation is a prospective, non-randomized, non-blinded study.

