8.8.5. Post-operative Treatment of Endoleaks

Type I and type III endoleaks warrant immediate treatment. Type II endoleaks should be treated at the physician's discretion, depending on aneurysm behavior and size, endoleak source, and time from implantation. If the aneurysm is enlarging, treatment by embolization or ligation should be considered. Type III endoleaks should be treated with additional ballooning or prostheses.

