8.9 Criteria and Procedures for Study Termination

A patient's follow-up in the study will end after:

- 1) Failure to deploy the device + 30 days;
- 2) Conversion to open surgical technique + 30 days;
- 3) Patient withdrawal or lost to follow-up;

- 4) Patient death;
- 5) Closure of the investigation; or
- 6) Completion of all scheduled clinical and imaging visits through 5 years.

No medical care related to the clinical study will be provided for the subjects after study completion.

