MI (Non-Q-Wave): Investigator identified patients having clinical evidence of a myocardial infarction with elevated peak CK values greater than or equal to three times the upper limit of normal with elevated CK-MB (above the institution's upper limit of normal) in the absence of new pathological Q-waves or clinical evidence of a myocardial infarction with troponin greater than three times the upper limit of normal, as determined by the investigator.

MI (Q-Wave): Post-procedure presence of new Q-waves greater than 0.04 seconds in at least two EKG leads.

Renal Failure: Acute or progressive renal insufficiency leading to the need for dialysis or hemofiltration.

Renal Insufficiency: A rise in serum creatinine of more than 30% above the pre-procedure level, resulting in a serum creatinine level >2.0 mg/dl that does not spontaneously resolve (does not include those patients with a pre-procedure serum creatinine >2.0 mg/dl).

Embolization: Clinical evidence of ischemic tissue remote from the operative field, presumably caused by thrombus dislodged from the aneurysmal sac, aortic neck, or adjacent vessels, including ischemia of the kidneys, pelvis (IIA) or lower limbs. This is, of course, distinct from intentional pre-operative, operative, or post-operative embolization procedures.

Graft Limb Occlusion: The presence of thrombus within one, or both, of the graft limbs (including any legs and extensions) creating complete occlusion with no blood flow through the graft limb.

Graft Lumen Diameter: The diameter measured inner wall to inner wall within the endograft.

Type I Endoleak: A peri-prosthetic leak occurring at the proximal and/or distal fixation zones.

Type II Endoleak: A leak caused by retrograde flow from patent lumbar or inferior mesenteric arteries or other collateral vessels.

Type III Endoleak: A leak caused by a defect in the graft fabric, or inadequate seal of modular graft components.

Type IV Endoleak: A leak caused by graft fabric porosity, often resulting in a generalized blush of contrast within the aneurysm sac.

Endoleak (early): Any endoleak observed within 30 days of device deployment.

Endoleak (late): Any endoleak observed later than 30 days after device deployment that was not documented during the first 30 days post-deployment.

Radiographic Migration

(stent-graft): Antegrade or retrograde movement of the stent-graft ≥ 10 mm at the level of the renal arteries as compared to the position on the first post-operative CT scan.

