Clinical Utility

Measures: Duration of procedural intubation; days to resumption of oral fluids; days to resumption of normal diet; days to resumption of normal bowel function; days to ambulation; duration of ICU stay; days to discharge.

Clinically Significant Migration

(stent-graft): Antegrade or retrograde movement of the stent-graft requiring surgical or endovascular intervention.

Barb Separation: Radiographic evidence of detachment of barbs from the stent strut as confirmed by the CEC.

Stent/attachment System

Fracture/break: Fracture or breakage of any portion of the stent or attachment system including metallic fracture or breakage of any suture material used to construct the stent or secure the stent or attachment system to the graft material as confirmed by the CEC.

Technical Success: Successful access of the aneurysm site and deployment of the Zenith Low Profile AAA Endovascular Graft and the Zenith Spiral-Z AAA Iliac Leg Graft in the intended location. The endovascular graft must be patent at the

time of deployment completion as evidenced by intraoperative angiography.

Device Success

(12-month):

Technical Success, with none of the following at 12 months:

- Type I or type III endoleaks requiring re-intervention;
- Graft limb occlusion;
- Aneurysm rupture or conversion to open surgical repair; or
- Aneurysm enlargement greater than 0.5 cm.

Major Adverse Events: All-cause death, Q-wave MI, renal failure requiring dialysis, paralysis, stroke, bowel ischemia, re-intubation.

Serious Adverse

Event:

An adverse event that led to death, led to a serious deterioration in the health of the subject that resulted in a life-threatening illness or injury, resulted in a permanent impairment of a body structure or a body function, required in-patient hospitalization or prolongation of existing hospitalization, resulted in medical or surgical intervention to prevent permanent impairment to body structure or a body function, led to fetal distress, fetal death, a congenital abnormality or birth defect.

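### Does the 12-month device success definition leave open whether a limb occlusion or type I/III endoleak resolved before the visit counts as a failure?

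*Combined protocol and SAP*

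**What the plan says.** Attachment 2 (Definitions) gives 12-month device success as "Technical Success, with none of the following at 12 months". It then lists type I or III endoleak needing re-intervention, graft limb occlusion, rupture or conversion to open repair, and enlargement above 0.5 cm. No component has a period of its own.

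Related text:

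- Attachment 2 describes limb occlusion as thrombus "creating complete occlusion with no blood flow through the graft limb" and does not mention a limb later reopened.
- Attachment 2 measures migration "as compared to the position on the first post-operative CT scan"; enlargement has no such reference.
- Section 8.8.5: "Type I and type III endoleaks warrant immediate treatment".
- Section 8.9 ends a patient's follow-up at "Conversion to open surgical technique + 30 days".
- Section 4.1: "The safety endpoint will be freedom from MAEs at 30 days".
- Section 4.2 lists reinterventions among the data to be evaluated, and also "Endoleak, change in aneurysm size, migration, device patency, device integrity".
- Sections 4.3 and 9.2 use the same endpoint name for this trial and for the historical 93.0% behind the 83% goal.

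**The concern.** One time phrase covers one-off events (rupture, conversion), a state (occlusion), a finding tied to an action (endoleak needing re-intervention) and a measurement (enlargement). Taken as status at the visit, it would forgive an occlusion or endoleak that was found and resolved earlier. Because section 8.8.5 calls for prompt treatment of type I and III endoleaks, such patients are foreseeable.

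Section 8.1 says "The current investigation is a prospective, non-randomized, non-blinded study", and the endpoint is tested against a fixed goal. If the scoring rule really were open, it could be settled after the results are known, and near the pass boundary one reclassified patient would decide the outcome. If the historical 93.0% had been counted on the other rule, the 83% goal would also not be comparable.

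**Working it through.** **1. The two readings, component by component**

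| Component | Status at the visit | Any occurrence through 12 months |
|---|---|---|
| Rupture, conversion | Unworkable: these are events, and follow-up stops 30 days after conversion, so an early conversion has no 12-month assessment | Works |
| Type I/III endoleak needing re-intervention | Nearly empty: early leaks are to be treated at once, so only those present at the 12-month scan would count | Works |
| Limb occlusion | Possible, from the definition's wording | Works |
| Enlargement > 0.5 cm | Natural, as a measurement | Possible |

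All four share one stem. The status reading fails for rupture and conversion and nearly empties the endoleak component.

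Two further comparisons point the same way. Freedom from MAEs at 30 days must mean through 30 days, since death or stroke on day 5 cannot be forgiven on day 30. The occlusion wording is also weak evidence for a status count: Attachment 2 defines Q-wave MI by the presence of new Q-waves, yet counts it as a major adverse event. Presence there is a diagnostic criterion, not a timing rule.

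**2. The plan's own figure**

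Section 9.1 states 59 patients for device success (goal 83%, expected 93.5%, exact binomial, one-sided 0.025, power 0.80). With those inputs the smallest exact size is 81 (at least 74 successes, power 84.4%). At 59 the rule is 55 or more successes, with power 66.2%; 59 appears as the smallest size only at one-sided 0.05. That is a separate matter and does not bear on the scoring rule. The steps below use the planned 120.

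**3. Decision rule at n = 120 evaluable**

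The critical count is the smallest c with P(X ≥ c | 120, 0.83) ≤ 0.025.

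- P(X ≥ 108) = 0.0222: passes.
- P(X ≥ 107) = 0.0412: fails.

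So c = 108, at most 12 failures. Power at 93.5% is P(X ≥ 108 | 120, 0.935) = 0.9514.

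**4. How much the reading could matter**

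Let d be the share of patients whose only failing event occurred and was resolved before 12 months. The documents give no d; 1, 2 and 3 points (1.2, 2.4 and 3.6 patients of 120) are assumptions. Every cumulative success is also a status success, so P(status passes, cumulative fails) is the difference between the two pass probabilities.

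| Scenario | d = 0 | d = 1 | d = 2 | d = 3 |
|---|---|---|---|---|
| (a) True cumulative rate 83%, scored by status: P(X ≥ 108) at 0.83 + d | 0.0222 | 0.0417 | 0.0746 | 0.1265 |
| (b) 93.5% is a status rate, scored cumulatively: P(X ≥ 108) at 0.935 − d | 0.9514 | 0.8843 | 0.7803 | 0.6478 |
| (b) Opposite verdicts: 0.9514 minus the line above | 0 | 0.0671 | 0.1711 | 0.3036 |
| (c) 93.5% is cumulative, scored by status: P(X ≥ 108) at 0.935 + d | 0.9514 | 0.9850 | 0.9970 | 0.9997 |
| (c) Opposite verdicts: the line above minus 0.9514 | 0 | 0.0336 | 0.0456 | 0.0483 |

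Scenario (a) puts the truth exactly at the goal, 10 points below the historical 93.0%; it illustrates type I error and is not an expected effect. Scenario (b) needs 93.5% to be a time-point rate, which no passage says. Scenario (c) is the ordinary reading: the trial passes with probability 95% or more however the events are scored. Even there, d = 3 would mean that 3 of 6.5 points, or 46% of all cumulative failures, were resolved before the visit.

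The expected count is 0.935 × 120 = 112.2. To turn 112 successes into a fail takes 112 − 107 = 5 reclassified patients, or 5/120 = 4.2% of the cohort.

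**The case for a change.** The strongest case for a change is that the inference from rupture and conversion does not formally settle occlusion, which is worded as a state, or enlargement, which is naturally judged at a scan. Attachment 2 can be explicit about time when it chooses: early and late endoleak are divided at 30 days, and migration has a named comparison scan. For enlargement, the pre-operative CT (allowed up to 6 months before implant under section 8.4) and the 30-day CT are both candidates and could classify the same patient differently. The independent events committee in section 8.13 is described as judging relatedness, not endpoint timing. With a boundary at 108 of 120, one patient can matter.

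What stands is that the rule and the enlargement baseline are not written in the visible text. What does not stand is that the two readings are equally open, or that a result would be wrong. Committee procedures and independent core laboratory imaging review (section 8.13) limit discretion, although they do not fix the timing rule. Because reinterventions, endoleak, patency and aneurysm size are all evaluated, a resolved event remains visible whichever way it is scored. Writing in a cumulative rule is not risk-free either: if the historical 93.0% had been a status count, it would create the very mismatch the concern warns of. The shared endpoint name gives no sign of different counting.

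**Conclusion.** The concern identifies unwritten detail, not an error. An analyst reading Attachment 2 as a whole would count an occlusion or a re-intervened type I/III endoleak at any time through 12 months as a failure, as must be done for rupture and conversion. Nothing shows that the historical rate was counted differently, and following the plan on this reading gives a valid test: actual one-sided level 2.2% and power 95.1% at 93.5% success with 120 evaluable patients.

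The largest adverse figures (65% power, 30% opposite verdicts) rest on two assumptions that the documents do not support: a 3-point share of resolved-only events and a planned rate that is a time-point rate. The 12.7% pass rate needs the same share and a true rate exactly at the goal. If 93.5% is the cumulative rate, the pass probability is at least 95% either way, and opposite verdicts occur at most 4.8% of the time for shares up to 3 points. The effect of the unnamed enlargement baseline cannot be sized from the documents. It too is a detail that analysts routinely settle when specifying the endpoint. No change to the plan follows.
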